9 SAFETY MONITORING AND REPORTING

The investigator is responsible for the monitoring and documentation of events that meet the criteria and definition of an AE or SAE as provided in this protocol.

9.1 Adverse Events

9.1.1 Definition and Reporting of an Adverse Event

An AE is defined as any unfavorable and unintended sign (including an abnormal laboratory finding), symptom, or disease (new or exacerbated) temporally associated with the use of a study drug, whether considered related to study drug or not.

Examples of AEs include:

- Worsening of a chronic or intermittent pre-existing condition including an increase in severity, frequency, duration, and/or has an association with a significantly worse outcome
- New conditions detected or diagnosed after study drug administration even though it may have been present before the start of the study
- Signs, symptoms, or the clinical sequelae of a suspected interaction
- Signs, symptoms, or the clinical sequelae of a suspected overdose of either study drug or a concurrent medication (overdose per se should not be reported as an AE or SAE)

When an AE or SAE occurs, it is the responsibility of the investigator to review all documentation (eg, hospital progress notes, laboratory results, and diagnostics reports) relative to the AE or SAE. The investigator will then record all relevant information regarding an AE or SAE in the eCRF. However, there may be instances when copies of medical records for certain cases are requested by the sponsor. In this instance, all patient identifiers will be blinded on the copies of the medical records prior to submission to the sponsor.

9.1.2 Assessment of Severity

The investigator will assess the severity for each AE and SAE reported during the study. AEs and SAEs should be assessed and graded based upon the NCI-CTCAE v5.0.

Toxicities that are not specified in the NCI-CTCAE will be defined as follows:

- Grade 1: Mild; asymptomatic or mild symptoms; clinical or diagnostic observations only; intervention not indicated
- Grade 2: Moderate; minimal, local or noninvasive intervention indicated; limiting age-appropriate instrumental activities of daily living
- Grade 3: Severe or medically significant but not immediately life-threatening; hospitalization or prolongation of hospitalization indicated; disabling; limiting self-care activities of daily living

- Grade 4: Life-threatening consequences; urgent intervention indicated
- Grade 5: Death related to AE

Note: The terms “severe” and “serious” are not synonymous. Severity is a measure of intensity (for example, grade of a specific AE, mild [Grade 1], moderate [Grade 2], severe [Grade 3], or life-threatening [Grade 4]), whereas seriousness is classified by the criteria based on the regulatory definitions. Seriousness serves as the guide for defining regulatory reporting obligations from the sponsor to applicable regulatory authorities as described in [Section 9.2](#).

9.1.3 Assessment of Causality

The investigator is obligated to assess the relationship between pamiparib and the occurrence of each AE or SAE using best clinical judgment. Alternative causes, such as natural history of the underlying diseases, concomitant therapy, and other risk factors, and the temporal relationship of the AE or SAE to pamiparib will be considered and investigated. The investigator should consult the [Pamiparib Investigator’s Brochure](#) in the determination of his/her assessment. There may be situations when an SAE has occurred, and the investigator has minimal information to include in the initial report to the sponsor. However, it is very important that the investigator always provides an assessment of causality for every SAE before transmission of the SAE report/eCRF to the sponsor because the causality assessment is one of the criteria used when determining regulatory reporting requirements. The investigator may change his/her opinion of causality based on follow-up information, amending the SAE report/eCRF accordingly.

The causality of each AE should be assessed and classified by the investigator as “related” or “not related.” An AE is considered related if there is at least “a reasonable possibility” that the AE may have been caused by pamiparib (ie, there are facts, evidence, or arguments to suggest possible causation, or a causal relationship between the AE and the drug cannot be ruled out). A number of factors should be considered in making this assessment, including:

- Temporal relationship of the AE to the administration of pamiparib/study procedure
- Whether an alternative etiology has been identified
- Mechanism of action of pamiparib
- Biologic plausibility
- An AE should be considered “related” to pamiparib if any of the following are met, otherwise the event should be assessed as “not related”:
 - There is clear evidence to suggest a causal relationship, and other possible contributing factors can be ruled out
 - There is evidence to suggest a causal relationship, and the influence of other factors is unlikely
 - There is some evidence to suggest a causal relationship (eg, the AE occurred within a reasonable time after administration of pamiparib). However, the

influence of other factors may have contributed to the AE (eg, the patient's clinical condition or other concomitant AEs).

- A causal relationship between the AE and the study drug cannot be ruled out

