8.2 Safety and Tolerability Assessments (Core and Extension Phases)

8.2.1 Adverse Events

Adverse event definitions, assignment of severity and causality, and procedures for reporting SAEs are detailed in [Section 9](#). The condition of each patient will be monitored from the time of signing the Informed Consent Form (ICF) to the end of the study. Patients will be observed for any signs or symptoms and asked about their condition by open questioning, such as “How have you been feeling since you were last asked?” at least once each day while a resident at the study site and at each study visit. Patients will also be encouraged to spontaneously report AEs occurring at any other time during the study. Any AEs, SAEs, and remedial action required will be recorded in the patient’s source data. The nature, time of onset, duration, and severity will be documented, together with a PI’s (or designee’s) opinion of the relationship to study drug. Adverse events recorded during the course of the study will be followed-up, where possible, until resolution. This will be completed at the PI’s (or designee’s) discretion.

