9.5.2 Completion and Transmission of the Serious Adverse Event Report

Once an investigator becomes aware that an SAE has occurred in a patient, he/she will report the information to the sponsor within 24 hours as outlined in [Section 9.5.1](#). The SAE report will always be completed as thoroughly as possible with all available details of the SAE and forwarded to the sponsor or designee within the designated timeframes. The paper SAE form, signed by the investigator, should be scanned and faxed and/or e-mailed to IQVIA. The original SAE form should then be filed appropriately, along with proof of reporting.

If the investigator does not have all information regarding an SAE, he/she is not to wait to receive additional information before notifying the sponsor or designee of the SAE and completing the form. The form will be updated when additional information is received.

The investigator will always provide an assessment of causality at the time of the initial report as described in [Section 9.1.3](#).

The sponsor will provide contact information for SAE receipt.

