9.6 Suspected Unexpected Serious Adverse Reactions and Expedited Reporting

A suspected unexpected serious adverse reaction is a serious adverse reaction that is both unexpected (ie, not present in the product's Reference Safety Information in the IB) and assessed as related to pamiparib either by the investigator or the sponsor. The sponsor will promptly assess the expectedness for all SAEs against the list of expected serious adverse reactions in the Reference Safety Information and expeditiously submit suspected unexpected serious adverse reactions to regulatory authorities, investigators, IRBs, and IECs based on applicable legislation.

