11.4 Safety Analysis

All AEs will be listed and summarized using descriptive methodology. The incidence of AEs for each treatment will be presented by severity and by association with the study drugs, as determined by the investigator. Each AE will be coded using MedDRA. Observed values for clinical laboratory evaluations data, 12-lead ECGs, and vital signs will be listed and summarized descriptively.

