18.1.1 Adverse Events

Adverse events will be classified using the Medical Dictionary for Regulatory Activities (MedDRA) classification system.

All adverse events (including non-treatment-emergent events) recorded on the CRF will be listed.

All AE summaries will include only treatment-emergent adverse events. Treatment-emergent adverse events are those AEs with an onset date on or after the date of first dose of study medication until the date of last study medication dose plus 30 days.

AEs will be categorized according to the following:

- Prior to Day 1 (thus not summarized, just listed)
- From Day 1 to the day prior to start rifampin or itraconazole dosing (category = pamiparib only)
- Part A: The day of start of rifampin dosing to the day prior to combined pamiparib and rifampin dosing (category = rifampin)
- Part A: At or after the day of coadministration until date of last dosing in core phase plus 30 days and before the administration of pamiparib in the Extension Phase (category = pamiparib with rifampin)

- Part B: The day of start of itraconazole dosing to the day prior to combined pamiparib and itraconazole dosing (category = itraconazole)
- Part B: At or after the day of coadministration until date of last dosing in core phase plus 30 days and before the administration of pamiparib in the Extension Phase (category = pamiparib with itraconazole)
- Extension Phase AEs

An overview of all AE will present the following frequencies by treatment and part:

- All treatment-emergent AEs
- Grade 3 or greater treatment-emergent AEs
- Treatment-related, treatment-emergent AEs
- Serious treatment-emergent AEs
- Serious, treatment-related treatment-emergent AEs
- Treatment-emergent AEs with an outcome of death
- Treatment-emergent AEs leading to discontinuation of study treatment

A breakdown of the number and percentage of patients reporting each adverse event, categorized by body system and preferred term, will be presented. Counting will be done by patient only, not by event; patients will only be counted once within each body system or preferred term.

A summary of drug related events reported, categorized by relationship to either study drug, will be provided. Patients with multiple events within a particular body system or preferred term will be counted once for a relation to study drug within that body system or preferred term.

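### The protocol's only causality criteria are for pamiparib, but the planned related-AE tables also need a judgement on rifampin and itraconazole

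*Protocol*

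**What the plan says.** **What is collected.** Protocol 9.1.3 states: "The investigator is obligated to assess the relationship between pamiparib and the occurrence of each AE or SAE". It asks for one related or not related classification per AE and points the investigator to the pamiparib Investigator's Brochure. An AE is related to pamiparib "if any of the following are met, otherwise the event should be assessed as" not related. Rifampin and itraconazole are not named there.

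Two other sections ask for a causality opinion. Protocol 8.2.1 wants the investigator's "opinion of the relationship to study drug" documented, but says: "Adverse event definitions, assignment of severity and causality, and procedures for reporting SAEs are detailed in" Section 9. Protocol 6.7 opens with a general request to judge relatedness to study drug. Its Core Phase paragraph then refers to AEs attributed to rifampin or itraconazole when it discusses entry to the Extension Phase. Neither section gives criteria.

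For SAEs, Protocol 9.5.2 says "The investigator will always provide an assessment of causality at the time of the initial report" and refers back to 9.1.3. The expedited-reporting test in 9.6 covers events "assessed as related to pamiparib either by the investigator or the sponsor".

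**What is to be reported.** Protocol 11.4 presents AEs "by association with the study drugs, as determined by the investigator". SAP 18.1.1 adds: "A summary of drug related events reported, categorized by relationship to either study drug, will be provided". It also plans rows for treatment-related and for serious treatment-related TEAEs, by treatment and part. The treatment categories include rifampin alone in Part A and itraconazole alone in Part B. The SAP does not define treatment-related, and SAP 7.1 declares no changes from the protocol.

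**The concern.** The tables call for an attribution that the protocol gives the investigator no criteria to make. An event judged to be a reaction to rifampin or itraconazole, with pamiparib excluded, has only one place to go under Protocol 9.1.3: not related. A treatment-related row for a rifampin-only period would then omit the events most plausibly caused by the drug being taken in that period.

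These tables serve the secondary objective on safety and tolerability of pamiparib given with rifampin or itraconazole. A reader of the study report would take the related rows to cover both drugs, because Protocol 11.4 and SAP 18.1.1 say so, while the underlying judgement might cover only one.

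**Working it through.** The plan states no figure to reproduce. The check is a comparison of sections, followed by simple arithmetic on what one patient is worth.

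**1. Does study drugs include the partner drugs?** The protocol's title page names pamiparib as the study drug. That narrow sense cannot explain the plural in Protocol 11.4 or the word either in SAP 18.1.1. Protocol 6.2 refers to rifampin or itraconazole together with pamiparib as both study drugs. The schedules in Appendix 1 list rifampicin and itraconazole dosing under study drug administration. The wider sense is the natural one for the planned tables.

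**2. Do any criteria cover the partner drugs?**

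| Section | Asks about | Gives criteria? |
|---|---|---|
| Protocol 9.1.3 | pamiparib | yes, for pamiparib |
| Protocol 8.2.1 | study drug | no; defers to Section 9 |
| Protocol 6.7 | study drug; mentions rifampin or itraconazole | no |
| Protocol 9.5.2 | SAE causality | no; refers to 9.1.3 |
| Protocol 9.6 | pamiparib | not for partner drugs |

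The last criterion in 9.1.3 does say study drug, but it sits under a lead-in about relatedness to pamiparib, so it does not extend the rule.

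**3. Which AEs would be lost?** Only those where pamiparib is ruled out and the partner drug is blamed. The 9.1.3 threshold is low, since an event counts as related if a causal role cannot be excluded. Such judgements are most plausible in the partner-only periods: Days 3 to 9 in Part A (7 of 12 Core Phase days) and Days 3 to 6 in Part B (4 of 9), from the label table in SAP 9.2.2. Protocol 1.2.1.1 gives a terminal half-life of about 13 hours, range 5.5 to 34. For the Day 1 pamiparib dose:

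- start of Day 3: 48/13 = 3.7 half-lives; at 34 hours, 48/34 = 1.4
- start of Day 9: 192/13 = 14.8 half-lives; at 34 hours, 192/34 = 5.6

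Late in the Part A rifampin period, an investigator could reasonably exclude pamiparib.

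**4. What is one patient worth?** SAP 18.1.1 counts patients, not events, and SAP 9.1.3 bases percentages on those exposed in the category. SAP 6.1 gives about 12 patients per part, with 10 expected to complete. If k patients have, in a given column, only drug-caused AEs attributed to the partner drug alone, the related row falls by 100 × k/N points:

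- N = 12, k = 1: 100/12 = 8.3 points
- N = 10, k = 1: 100/10 = 10 points

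The documents give no reaction rate for rifampin or itraconazole, so k is unknown, and k = 0 (no shift) is possible.

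**5. Does the gap end with the Core Phase?** Not necessarily. SAP 18.1.1 closes the coadministration category when Extension Phase pamiparib starts. No minimum interval after the last partner-drug dose is stated, and Protocol 4.2 says induction after rifampin can last several weeks. A partner-drug reaction could therefore have its onset in the Extension Phase category.

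**The case against.** The strongest reply is that the CRF may already hold a causality field for each drug. SAP 3.0 says the plan was written from the final CRF of 19 August 2019, and SAP 9.1.3 says categories will appear in tables as they do in the CRF or database. A SAP author with that form in hand who plans a summary by either study drug may well have seen two fields. This is fair: it suggests per-drug collection without proving it. Even so, the second field would have no criteria behind it, and treatment-related would remain undefined.

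It can also be said that Protocol 9.1.3 is not the only causality instruction. That is correct. A reader might infer that the protocol never asks for partner-drug attribution at all, but 6.7 and 8.2.1 ask about study drug, and 6.7 presupposes attribution to rifampin or itraconazole. What is missing is a stated basis for that judgement.

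Third, the objective concerns pamiparib when coadministered, so pamiparib-centred causality is defensible, and the pamiparib-only test in 9.6 serves expedited reporting rather than these tables. Both points stand. They would support limiting the tables to pamiparib-related AEs, but the tables as planned are not so limited.

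Finally, every AE is listed, no hypothesis is tested, and the parts are small enough to read event by event. This stands and limits the severity.

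**Conclusion.** The inconsistency is real and minor. The protocol's causality criteria cover pamiparib only, while Protocol 11.4, Protocol 6.7 and SAP 18.1.1 rely on attribution to the partner drug as well. The loss of events from the related-AE tables rests on two conditions: that 9.1.3 is applied as written, and that the CRF has a single causality field.

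Two stronger readings are not supported. One is that partner-drug causality was not collected; without the CRF that cannot be said. The other is that the related-AE rates are understated by some stated range; the documents allow a per-patient value (about 8 points at 12 patients, 10 at 10) but no estimate of how many patients are affected.

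The effect is confined to descriptive related-AE outputs. Columns are assigned by treatment at onset, so a pamiparib-related event in a rifampin column is not mislabelled. PK results, all-TEAE and grade summaries are unchanged, and every event still appears in the listings.

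**What to change.** 1. Amend Protocol 9.1.3 so that the investigator records causality separately for pamiparib and for the coadministered drug (rifampin in Part A, itraconazole in Part B). Apply this to every AE and SAE from the first partner-drug dose until 30 days after the last one, including AEs with onset after Extension Phase pamiparib has begun.
2. Confirm that the CRF holds both fields, or add the missing one.
3. In SAP 18.1.1, define treatment-related as related to either drug, and tabulate related TEAEs by pamiparib, by partner drug and by either.

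If only pamiparib causality was collected, label the rows pamiparib-related, drop the either-drug summary, and reconcile Protocol 11.4 and 6.7 with 9.1.3.

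The cost is some protocol wording, one SAP definition, one table layout and possibly one CRF field. The downside is one extra judgement per AE at the site. The fallback avoids new data collection but still needs the protocol sections brought into line.

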9.1.4 Follow-Up of Adverse Events

After the initial AE or SAE report, the investigator is required to proactively follow each patient and provide further information to the sponsor on the patient's condition.

All AEs and SAEs documented at a previous visit/contact and designated as ongoing will be reviewed at subsequent visits/contacts.

All AEs and SAEs will be followed until resolution, the condition stabilizes or is considered chronic, the AE or SAE is otherwise explained, the patient is lost to follow-up, or the patient withdraws consent. Once resolved, the appropriate AE or SAE eCRF page(s) will be updated. The investigator will ensure that follow-up includes any supplemental investigations as may be indicated to elucidate the nature and/or causality of the AE or SAE. This may include additional laboratory tests or investigations, histopathologic examinations, or consultation with other health care professionals.

The sponsor may request that the investigator perform or arrange for the conduct of supplemental measurements and/or evaluations to elucidate as fully as possible the nature and/or causality of the AE or SAE. The investigator is obligated to assist. If a patient dies during participation in the study or during a recognized follow-up period, the sponsor will be provided with a copy of any postmortem findings, including histopathology, if conducted.

New or updated information will be recorded on the originally completed SAE report/eCRF, with all changes SAE form changes signed and dated by the investigator. The updated SAE follow-up report/eCRF should be re-sent to the sponsor within the time frames outlined in [Section 9.5.1](#).

If a patient is lost to follow-up, study center personnel must do their utmost to re-establish contact with the patient. All measures taken to follow up with the patient should be recorded.

Should attempts to contact the patient by telephone be unsuccessful, the following additional attempts should be made to obtain protocol-required follow-up information. The patient should be contacted by mail in a manner that provides proof of receipt by the patient. If unsuccessful, other contacts should be explored, such as referring physicians or relatives. Attempts of contact should be documented in the patient's source documents. If a patient cannot be contacted despite all attempts, the patient will be considered lost to follow-up, and death information should be obtained through a public record search if local agencies permit.

9.1.5 Laboratory Test Abnormalities

Abnormal laboratory findings (eg, chemistry, hematology, or coagulation) or other abnormal assessments (eg, ECGs, x-rays, or vital signs) that are judged by the investigator as clinically

significant will be recorded as AEs or SAEs. This includes clinically significant abnormal laboratory findings or other abnormal assessments that are present at baseline and significantly worsen during the study. The definition of clinically significant is entrusted to the judgment of the investigator. In general, these are the abnormalities that:

- Are associated with clinical signs or symptoms, or
- Require active medical intervention, or
- Lead to dose interruption or discontinuation, or
- Require close observation, more frequent follow-up assessments, or
- Further diagnostic investigation

9.2 Definition of a Serious Adverse Event

An SAE is any untoward medical occurrence that, at any dose:

- Results in death
- Is life-threatening

Note: The term “life-threatening” in the definition of “serious” refers to an AE in which the patient was at risk of death at the time of the AE. It does not refer to an AE that hypothetically might have caused death if it were more severe.

- Requires hospitalization or prolongation of existing hospitalization

Note: In general, hospitalization signifies that the patient was admitted (usually involving at least an overnight stay) to the hospital or emergency ward for observation and/or treatment that would not have been appropriate in the physician’s office or outpatient setting. Complications that occur during hospitalization are AEs. If a complication prolongs hospitalization or fulfills any other serious criteria, the AE is serious. When in doubt as to whether “hospitalization” occurred or was necessary, the AE should be considered serious.

- Results in disability/incapacity

Note: The term disability means a substantial disruption of a person’s ability to conduct normal life functions. This definition is not intended to include experiences of relatively minor medical significance, such as uncomplicated headache, nausea, vomiting, diarrhea, influenza, and accidental trauma (eg, sprained ankle), which may interfere with or prevent everyday life functions but do not constitute a substantial disruption.

- Is a congenital anomaly/birth defect
- Is considered a significant medical AE by the investigator based on medical judgment (eg, may jeopardize the patient or may require medical/surgical intervention to prevent one of the outcomes listed above)

The following are NOT considered SAEs:

- Hospitalization for elective treatment of a pre-existing condition that did not worsen from

baseline

- Hospitalization for social/convenience considerations
- Scheduled therapy for the target disease of the study, including admissions for transfusion support or convenience

